6.2 DURATION OF STUDY PARTICIPATION

6.2.1 Duration of study participation for each patient

LTS12551 study consists of 3 periods (See [Section 10](#)):

Enrollment period: Combined V1/V2 Visit: Eligible patients from PDY14192, EFC13579, and EFC13691 studies should rollover into LTS12551 the same day as *the end-of-treatment visit of the parent study*.

Note: A screening period of 0 to 3 weeks was proposed only for patients rolling over from DRI12544. Enrollment from Study DRI12544 is complete, thus the screening period does not apply anymore.

Treatment period: 48 or 96 weeks open-label treatment.

Patients enrolled prior to Amendment 04 approval, will continue to participate in the 2-year treatment duration; patients enrolled after Amendment 04 approval will participate in the 1-year treatment duration. During the open-label treatment period, patients will continue taking their background controller therapy, as maintained during the parent study or as modified based on Investigator's judgment.

Post-treatment period: 12 weeks.

Upon completion of the open-label treatment period (or following early discontinuation of Investigational Medicinal Product [IMP]) patients will continue into the post-treatment period. During this period, patients will continue their background controller therapy, as maintained during the open-label treatment period or as modified based on Investigator's judgment (eg, taking into account the reduction of dupilumab levels over time upon completion of the treatment period).

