10.1.1.16 Visit 17 (End-of-Treatment: Month 24, Week 96)

End-of-Treatment Visit is scheduled 2 weeks after the last IMP administration.

- Record all medication use with start dose in e-CRF including starting dose.
- Inquire about AEs/SAEs and background asthma therapy tolerability.
- Measure vital signs (blood pressure, heart rate, respiration rate, body temperature, weight).
- Perform physical examination.
- Administer health care resource utilization questionnaire.
- Perform spirometry
 - Spirometry will be performed after withholding the last dose of salbutamol/albuterol or levosalbutamol/levalbuterol for at least 6 hours and withholding the last dose of LABA for at least 12 hours (ultra-LABA like vilanterol should be withheld for at least 24 hours) and withholding the last dose of LAMA for at least 24 hours prior to administration of investigational product. This will be verified before performing the measurements.
- Perform 12-lead ECG.
- Perform blood sampling for:
 - Clinical laboratories.
 - Serum sample (predose) for PK and anti-dupilumab antibody analysis.
 - Hepatitis B viral load testing: For patients in Japan (or other countries/regions if there is local regulatory requirement) who were HBsAg negative and HBsAb positive at screening during the parent study, or at the additional test due to Local Amendment 03 (Japan).
- 
- Perform urine pregnancy test (for women of childbearing potential).
- Obtain urine for urinalysis (dipstick).
- Call IVRS/IWRS to register the EOT date.
- Schedule appointment for next visit and remind patient to withhold the last dose of salbutamol/albuterol or levosalbutamol/levalbuterol for at least 6 hours and withholding the last dose of LABA for at least 12 hours (ultra-LABA like vilanterol should be withheld for at least 24 hours) and withholding the last dose of LAMA for at least 24 hours prior to the next visit.
- Remind patient to continue the background therapy.
- Remind patients to arrive for next visit in fasting state.
- Perform monthly telephone contact with patient after Week 24 (Visit 11) to collect safety information.

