10.1.2.12 Visit 17 (End-of-Treatment: Month 12, Week 48)

End-of-Treatment visit is scheduled 2 weeks after the last IMP administration.

- Record all medication use with start dose in e-CRF including starting dose.
- Inquire about AEs/SAEs and background asthma therapy tolerability.
- Measure vital signs (blood pressure, heart rate, respiration rate, body temperature, weight).
- Perform physical examination.
- Administer paper ACQ-5 and AQLQ(S).
- Administer health care resource utilization questionnaire.
- Perform spirometry:
 - Spirometry will be performed after withholding the last dose of salbutamol/albuterol or levosalbutamol/levalbuterol for at least 6 hours and withholding the last dose of LABA for at least 12 hours (ultra-LABA like vilanterol should be withheld for at least 24 hours) and withholding the last dose of LAMA for at least 24 hours prior to administration of investigational product. This will be verified before performing the measurements.
- Perform 12-lead ECG.
- Perform blood sampling for:
 - Clinical laboratories.
 - Serum sample (predose) for PK and anti-dupilumab antibody analysis.
 - Hepatitis B viral load testing: For patients in Japan (or other countries/regions if there is local regulatory requirement) who were HBsAg negative and HBsAb positive at

screening during the parent study, or at the additional test due to Local Amendment 03 (Japan).

- [REDACTED]
- Perform urine pregnancy test (for women of childbearing potential).
- Obtain urine for urinalysis (dipstick).
- Call IVRS/IWRS to register the EOT date.
- Schedule appointment for next visit and remind patient to withhold the last dose of salbutamol/albuterol or levosalbutamol/levalbuterol for at least 6 hours and withholding the last dose of LABA for at least 12 hours (ultra-LABA like vilanterol should be withheld for at least 24 hours) and withholding the last dose of LAMA for at least 24 hours prior to the next visit.
- Remind patient to continue the background therapy.
- Remind patients to arrive for next visit in fasting state.
- Perform monthly telephone contact with patient after Week 24 (Visit 11) to collect safety information.

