11.3.2 Safety population

The primary analysis population is the safety population, which is defined as all patients who have actually received at least one dose or part of a dose of dupilumab in the LTS12551 study.

The treatment-emergent period is defined as the time from the first dose of dupilumab in LTS12551 up to the last dose of dupilumab plus 2 weeks (corresponding to one dose interval) plus 12 weeks (follow-up period duration). The pre-treatment period is defined as the time from the starting of AE reporting in LTS12551 study up to the first dose of dupilumab in LTS12551.

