1 OVERVIEW AND INVESTIGATIONAL PLAN

1.1 STUDY DESIGN AND RANDOMIZATION

LTS12551 is a multinational, multicenter, 1-year (48 weeks) or 2-year (96 weeks) single arm extension study to evaluate the long-term safety and tolerability of dupilumab in patients with asthma, who completed the treatment and follow-up period in the DRI12544 study, or who completed the treatment period in the EFC13579, EFC13691 or PDY14192 studies.

In the LTS12551 study, dupilumab 300 mg is administered subcutaneously (SC) every 2 weeks (q2w), as an add-on therapy to a variety of allowable combinations between inhaled corticosteroid (ICS) and other controller medications as maintained during the parent study, including the oral corticosteroids (OCS) medication for the patients from the EFC13691 study. The LTS12551 consists of three periods:

- Screening Period (0-3 weeks, if applicable)
- Treatment Period (48 weeks open-label period for the patients enrolled after the protocol amendment 4, or 96 weeks open-label period for the patients enrolled before the protocol amendment 4)
- Post-treatment Period (12 weeks, dupilumab-free follow-up period)

The 4 parent studies are described briefly as follows:

DRI12544: A phase 2b, randomized, double-blind, placebo-controlled, dose ranging, parallel group study comparing different doses and regimens of dupilumab SC for 24 weeks in patients with moderate to severe, uncontrolled asthma. Patients were randomized in ratio of 1:1:1:1:1 into 5 arms, dupilumab 200 mg every 4 weeks (q4w), dupilumab 300 mg q4w, dupilumab 200 mg q2w, dupilumab 300 mg q2w, and placebo. Patients were allowed to administer moderate- or high-dose inhaled corticosteroid (ICS) in combination with long-acting beta agonist (LABA) as follows: mometasone furoate / formoterol, budesonide / formoterol, and fluticasone propionate / salmeterol in the treatment period, and continued with the stable dosage of controller medications in the 16-week post-treatment follow-up period. There were 776 patients enrolled in DRI12544.

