PDY14192: A phase 2a, exploratory, randomized, double-blind, placebo-controlled study of the effects of dupilumab 300 mg q2w SC for 12 weeks on airway inflammation of adults with persistent asthma. Patients are randomized in a ratio of 1:1 to dupilumab 300 mg q2w and placebo q2w. Patients undergo two bronchoscopy procedures respectively before treatment and at the end of treatment period, each of which is followed with an oral prednisone 40 mg daily treatment for 3 (up to 5) days. Patients are allowed to administer a background therapy of medium to high dose ICS in combination with a second controller medication (LABA), and potentially plus a third controller medication (eg, LAMA, LTRA). There are in total 42 patients planned for PDY14192.

Parent study	Sample size	Treatment arms	Treatment duration	
		Dupilumab 300 mg q2w,		
		Dupilumab 200 mg q2w,	24 weeks	
DRI12544	776	Dupilumab 300 mg q4w,		
		Dupilumab 200 mg q4w,		
		Placebo q2w (2 mL in matched 5 mL vials)		
	1902	Dupilumab 300 mg q2w,		
EEC12570		Placebo q2w matching 300 mg q2w (2 mL in matched pre-filled syringe),	52 weeks	
EFC15579		Dupilumab 200 mg q2w,	J2 WEEKS	
		Placebo q2w matching 200 mg q2w (1.14 mL in matched pre-filled syringe)		
EFC13691	210	Dupilumab 300 mg q2w, Placebo q2w (2 mL in matched pre-filled syringe)	24 weeks	
PDY14192	42	Dupilumab 300 mg q2w, Placebo q2w (2 mL in matched pre-filled syringe)	12 weeks	

Patients from DRI12544 who completed the 24-week treatment period and 16-week follow-up period might be eligible for enrolling into LTS12551 at the end of study (EOS) visit of DRI12544 or thereafter. The screening period (Visit 1 and Visit 2) of LTS12551, and a 600 mg loading dose on Day 1 were only applicable for patients coming from DRI12544, as those patients experienced a gap in dosing for at least 16 weeks. According to the original protocol of LTS12551, patients coming from DRI12544 (non-US) could combine the EOS visit of DRI12544 with Visit 1/Visit 2 of LTS12551; according to the amended protocol 1, Visit 1 and Visit 2 of LTS12551 should be independent from the EOS visit of DRI12544. Thus, after the protocol amendment 1 became effective in LTS12551, patients from DRI12544 should be screened starting at Visit 1 (for 7 to 21 days) in LTS12551 before dosing started at Visit 2.

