2.1.4 Safety endpoints

The primary endpoint of this study is the number (n) and percentage (%) of patients experiencing any treatment-emergent adverse events (TEAE). Adverse Events (AEs), Serious Adverse Events (SAEs), Adverse Events of Special Interest (AESI), adverse events leading to treatment discontinuation are collected at each visit from the time of informed consent signature to the end of study. The safety analysis will be based on the reported adverse events and other safety information, such as clinical laboratory data, vital signs, and ECG.

Observation period

The observation period will be divided into 4 epochs:

- The screening epoch is defined as the time period prior to the date/time of the first dose of IMP in LTS12551.
- The **treatment** epoch is defined as the time period from the date/time of the first dose of IMP to the date/time of the last dose of IMP + 14 days.
- The **follow-up** epoch is defined as the time period from the date/time of the last dose of IMP + 15 days to the end date of 12-week post-treatment follow-up period.
- The **post-study** epoch is defined as the time period from the end date of 12-week post-treatment follow-up period + 1 day.

The **treatment - emergent adverse event period** will include both the **treatment** epoch and **follow-up** epoch. If applicable, the **post-treatment-emergent adverse event period** will be the post-study epoch.

The **pre-treatment adverse event period** will be from starting time of AE reporting up to the first dose of IMP in the LTS12551 study. For all the periods aforementioned, both date and time shall be used in the determination of the periods, as long as they will be available.

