2.4.5.1 Analyses of adverse events

Generalities

The primary endpoint of this study is the number (n) and percentage (%) of patients experiencing any treatment-emergent adverse events (TEAE). Pre-treatment (if applicable) adverse events will be described separately.

If an adverse event date/time of onset (occurrence, worsening, or becoming serious) is incomplete, an imputation algorithm will be used to classify the adverse event as pre-treatment or treatmentemergent adverse event. The algorithm for imputing date/time of onset will be conservative and will classify an adverse event as treatment-emergent, unless there is definitive information to determine it is pre-treatment. Details on classification of adverse events with missing or partial onset dates are provided in Section 2.5.

Adverse event incidence tables will be presented by system organ class (SOC), high level group term (HLGT), high level term (HLT) and preferred term (PT) sorted in alphabetical order, to summarize the number (n) and percentage (%) of patients experiencing at least an AE by the treatment category and overall (see Section 2.3.2). Multiple occurrences of the same event in the same patient will be counted only once in the tables within a treatment category. The denominator for computation of percentages is the safety population within each treatment category. In all AE incidence tables, the total patient years (in the unit of 100 patient-years) for each treatment category and overall (see Section 2.3.2) will be presented in the corresponding column headers.

The number of events per 100 patient-years (adjusted for the total duration of exposure) by the treatment category and overall (see Section 2.3.2) will be presented for each AESI during the treatment-emergent period.

The table of all treatment-emergent adverse events presented by SOC and PT will be sorted by the internationally agreed SOC order (from MedDRA) and decreasing frequency of PTs within SOCs. Sorting will be based on the results for the overall patients across treatment categories, unless otherwise specified.

Analysis of all treatment-emergent adverse events

The following treatment-emergent adverse event summaries by the treatment category and overall patients (see Section 2.3.2) will be generated for the safety population. Sorting will be based on the results for the overall patients across treatment categories, unless otherwise specified.

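### Crude any-TEAE and SAE percentages pool planned risk windows of 60 and 108 weeks, with no figure at an equal horizon

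*SAP*

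**What the plan says.** SAP 2.1.4 states: "The primary endpoint of this study is the number (n) and percentage (%) of patients experiencing any treatment-emergent adverse events (TEAE". In the adverse event tables of SAP 2.4.5.1, "The denominator for computation of percentages is the safety population within each treatment category". Any TEAE, treatment-emergent SAEs and the SOC/PT tables are all reported this way.

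Two treatment durations run in one study. SAP 1.1 describes a "48 weeks open-label period for the patients enrolled after the protocol amendment 4, or 96 weeks open-label period for the patients enrolled before" the amendment. The treatment-emergent period starts at the first dose and, in Protocol 11.3.2, runs "up to the last dose of dupilumab plus 2 weeks (corresponding to one dose interval) plus 12 weeks (follow-up period duration"). SAP 2.1.4 builds the same window from its treatment and follow-up epochs. On both schedules the last dose falls two weeks before the end-of-treatment visit: "End-of-Treatment Visit is scheduled 2 weeks after the last IMP administration" (Protocol 10.1.1.16, Week 96) and "End-of-Treatment visit is scheduled 2 weeks after the last IMP administration" (Protocol 10.1.2.12, Week 48).

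The amended protocol notes in 6.2.1: "Enrollment from Study DRI12544 is complete, thus the screening period does not apply anymore". The DRI12544 patients therefore all entered before Amendment 04.

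Under SAP 2.3.2, non-OCS results appear by parent study, by prior arm within parent study, and as 'All'. No column separates the two durations. SAP 2.4.5.1 puts total patient-years in the headers of the adverse event tables. It plans events per 100 patient-years and Kaplan-Meier estimates at Weeks 4, 12, 24, 48 and 60, but only for AESIs and other selected groupings.

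**The concern.** A crude percentage with at least one event can only rise as the window lengthens. If two groups have the same underlying risk and one is watched for 108 weeks and the other for 60, the first can show the higher percentage for that reason alone. Three readings are exposed: the DRI12544 column beside the other parent studies, any column that holds both schedules (possibly including those for EFC13691), and the non-OCS 'All' figure, whose value depends on how many patients enrolled before the amendment.

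The any-TEAE percentage is the headline result of a study meant to describe long-term safety. The reader can see that follow-up differs but has no any-TEAE or SAE risk at one common time.

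**Working it through.** **1. Planned windows.** The protocol synopsis gives maximum durations of 108 and 60 weeks (111 with DRI12544 screening). These reproduce: 96 + 12 = 108 and 48 + 12 = 60. The treatment-emergent window agrees. The last planned dose is at Week 94 or 46, so 94 + 2 + 12 = 108 and 46 + 2 + 12 = 60. The ratio is 108/60 = 1.8. These are planned maxima; early stopping or an interim cut-off shortens them.

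**2. Share on the longer plan (assumed).** SAP 1.1 and 1.3 give 776 + 1902 + 210 + 42 = 2930, which reproduces the SAP's maximum. Without EFC13691, 2930 − 210 = 2720. If every DRI12544 patient rolled over and nobody else was on 96 weeks, the share is s = 776/2720 = 28.5%. With 60% rollover from DRI12544 and full rollover elsewhere, it is 466/(466 + 1902 + 42) = 19.3%. Parent-study sizes are not rollover counts, and the protocol synopsis expects only about 2206 patients in total, so s is illustrative.

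**3. Effect on the percentage (assumed hazards, full follow-up).** Let p be the 60-week risk.

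- Constant hazard: p108 = 1 − (1 − p)^1.8.
- Hazard halved after Week 60: the exponent is (60 + 48/2)/60 = 1.4.
- Non-OCS 'All' = p + s(p108 − p), with s = 28.5%.

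| p | p108, constant | 'All', constant | p108, halved | 'All', halved |
|---|---|---|---|---|
| 10% | 17.3% | 12.1% | 13.7% | 11.1% |
| 50% | 71.3% | 56.1% | 62.1% | 53.5% |
| 70% | 88.5% | 75.3% | 81.5% | 73.3% |
| 90% | 98.4% | 92.4% | 96.0% | 91.7% |

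At p = 70% and constant hazard, 'All' is 73.6% for s = 19.3% and 76.5% for s = 35%. If no first events occur after Week 60, p108 = p and there is no effect.

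**4. Can header patient-years repair it?** Full exposure is 48 × 7/365.25 = 0.92 or 96 × 7/365.25 = 1.84 patient-years. With p = 70% and constant hazard, dividing patients with an event by exposure gives 70/0.92 = 76 and 88.5/1.84 = 48 per 100 patient-years, although the hazard is identical. With p = 10% the figures are 10/0.92 = 10.9 and 17.3/1.84 = 9.4, which is much closer. The division is a tolerable approximation for uncommon events and misleading for common ones.

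The SAP does not say which patient-years the headers use. The exposure definition in SAP 2.4.3.1 (last dose minus first dose plus 14 days) would cover 48/60 = 80% or 96/108 = 89% of the window in which TEAEs count.

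**5. Does the proposed remedy work?** Under either hazard pattern, Kaplan-Meier incidence at Week 48 is 1 − (1 − p)^0.8 in both cohorts: 8.1%, 42.6% and 61.8% for p = 10%, 50% and 70%. Patients with a first event per 100 patient-years at risk, at p = 70%, come to 104.7 in both cohorts under constant hazard. They come to 104.7 against 91.8 if the hazard halves after Week 60.

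**The case against.** The strongest reply is that the SAP already shows unequal follow-up and that nobody plans to test these columns. SAP 2.4.5 calls the safety analysis essentially descriptive. Header patient-years, exposure bands and parent-study columns let a careful reader see the imbalance, and for uncommon events a reader can form a rough rate. AESIs and selected groupings have Kaplan-Meier estimates and rates. SAP 1.6 says few patients from the other parent studies had data on the endpoints dropped by Amendment 04. That suggests, without stating a split, that the parent-study columns largely separate the two durations.

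An equal horizon would also not make DRI12544 comparable with the rest. "Patients from DRI12544 who completed the 24-week treatment period and 16-week follow-up period might be eligible for enrolling into LTS12551", so those patients had a dosing gap and received a loading dose.

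Most of this stands, and it keeps the point small. The SAP 1.6 remark also argues against assuming that half or more of 'All' is on 96 weeks. The reply does not supply an any-TEAE or SAE risk at a common time, and for a common event the header patient-years cannot recover one (step 4). Separate parent-study columns do not stop the 'All' percentage from moving with the enrolment mix.

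A reader might infer that the SAP ignores unequal follow-up altogether. It does not: the right method is already there, applied to secondary groupings and not to the primary endpoint.

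**Conclusion.** The point holds as a limit on interpretation. The planned windows of 60 and 108 weeks, the crude denominator and the restriction of Kaplan-Meier and rates to AESIs and selected groupings all follow directly from the documents. The size does not, because neither the 48/96-week split nor any TEAE risk is given. Under constant hazard, full follow-up and a 28.5% share, the non-OCS 'All' figure moves by about 2 to 6 percentage points for 60-week risks of 10% to 90%. It moves less if the hazard falls, and not at all if no first events occur after Week 60.

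Two stronger readings are not supported. One is that the primary endpoint is invalid: it is a clearly defined descriptive count with no test attached. The other is that the contrast between prior placebo and prior dupilumab within a parent study is distorted. Planned duration follows enrolment date, not prior arm, and the parent studies were randomised, so that contrast should be little affected.

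**What to change.** Keep crude n (%) as the endpoint. In SAP 2.4.5.1:

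- Add Kaplan-Meier cumulative incidence at Week 48 for any TEAE and any treatment-emergent SAE, in the existing columns, for the interim and final reports. Censor at the end of the treatment-emergent period or at the data cut-off, and state that this assumes non-informative censoring. Week 48 is on the SAP's own grid and 12 weeks inside the shorter window, whereas Week 60 is that window's planned end.
- As optional support, give patients with a first event per 100 patient-years at risk for the same two endpoints. Note that this is free of duration only under constant hazard, so it does not replace the Week 48 figure.
- State that the header patient-years follow the exposure definition in SAP 2.4.3.1, or define them over the full treatment-emergent period.

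The cost is SAP wording and a few extra tables, from data already collected and with a method the SAP already uses.

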11.4.3.1.2 Adverse Events of Special Interest

The following summaries will be generated:

- Incidence of each AESI will be tabulated.
- The time-to-first event analyzed using Kaplan-Meier methods and displayed as Kaplan-Meier plots (cumulative incidence [%] versus time based on Kaplan-Meier estimates) will be provided to depict the course of onset over time. Number of treatment-emergent AESIs per 100 patient-years (total number of events adjusted for the total duration of exposure) will be presented by decreasing incidence of PT.
- An overview summary of the number (%) of patients with:
 - Any TEAE.
 - Any serious AE (regardless of treatment-emergent status).

- Any treatment-emergent SAE.
- Any AE leading to death.
- Any TEAE leading to permanent study drug discontinuation.
- Any TEAE by maximum intensity, corrective treatment, and final outcome.
- Cumulative incidence (Kaplan-Meier estimates) up to specified time points.

AESI definitions and the method to identify AESIs will be specified in the SAP.

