2.1.3.1 Severe Exacerbation Events

A severe exacerbation event during the study is defined as any of the following:

- Use of systemic corticosteroids for \geq 3 days.
 - At least double the dose of systemic corticosteroids for patients enrolling from EFC13691 who are currently on systemic corticosteroids.
- Or, hospitalization or emergency room visit because of asthma, requiring a systemic corticosteroid treatment.

The severe exacerbation events are collected on eCRF page "Asthma exacerbations event". Only events confirmed on eCRF page will be used in the analysis.

Both number and annualized rate of severe exacerbation events will be analyzed. The annualized event rate is defined as the number of severe exacerbation events per patient-year. Number and annualized rate will also be analyzed for severe exacerbation with use of systemic corticosteroids for \geq 3 days only, and that with hospitalization or with emergency room visit only. The mean duration of a severe exacerbation will also be summarized.

For the treatment period, total number of events and standardized on-treatment duration will be calculated for each patient:

• The total number of events is defined as the number of events that are onset between the date of first IMP dose in LTS12551 study and the date of last IMP dose in LTS12551 study + 14 days;

The standardized on-treatment duration (in years) is calculated by (the date of last IMP dose in LTS12551 study – the date of first IMP dose in LTS12551 study + 14 days)/365.25.

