2.4.3.1 Extent of investigational medicinal product exposure

The extent of IMP exposure will be assessed by the duration of IMP exposure in LTS12551 study.

Duration of investigational product exposure is defined as: the last IMP dose date in LTS12551 study – the first IMP dose date in LTS12551 study + 14 days, regardless of unplanned intermittent discontinuations (see Section 2.5.3 for calculation in case of missing or incomplete data).

Duration of IMP exposure will be summarized descriptively as a quantitative variable (number, mean, SD, median, minimum, and maximum). In addition, duration of treatment exposure will also be summarized categorically by counts and percentages for each of the following categories and cumulatively according to these categories (the categories exceeding Week 48 may apply to only the patients on the 96-week treatment period who signed the informed consent form before the approval of protocol amendment 4):

 \leq 4 week

- > 4 and \leq 12 weeks
- > 12 and ≤ 24 weeks
- > 24 and ≤ 48 weeks
- > 48 and \leq 72 weeks
- > 72 and \leq 96 weeks
- >96 weeks

Additionally, the cumulative duration of treatment exposure, will be provided in patient years by treatment category and overall (see Section 2.3.2).

Number and percentage of patients will be summarized by total number of injections they received during the LTS12551 study. The number and percentage of patients who receive injection will be summarized by type of administrator (site staff, patient or non-professional care giver, professional care giver at home), by dosing week, and maybe by IMP packaging way (vial or pre-filled syringe).

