Notes for the last two bullets: when TEAE start date or worsening date is partially available, the maximum of the earliest possible TEAE start date and the treatment start date will be used. When TEAE start date or worsening date is completely missing, the treatment start date will be used.

• Number of treatment-emergent AESIs and other selected AE groupings per 100 patientyears (total number of events adjusted for the total duration of exposure) will be presented by decreasing incidence of PT within each AESI and other selected AE groupings category.

Analysis of pre-treatment adverse events

- All pre-treatment AEs by primary SOC and PT, showing the number (%) of patients (including total patient years in column headers) with at least one pre-treatment AE, will be presented by the internationally agreed SOC order and by decreasing incidence of PTs within each SOC.
- All pre-treatment SAEs by primary SOC and PT, showing the number (%) of patients (including total patient years in column headers) with at least one pre-treatment SAE, will be presented by the internationally agreed SOC order and by decreasing incidence of PTs within each SOC.
- All pre-treatment adverse events leading to study discontinuation by primary SOC and PT, showing the number (%) of patients (including total patient years in column headers), will be presented by the internationally agreed SOC order and by decreasing incidence of PTs within each SOC.

Analysis of adverse events

• All pre-treatment, treatment-emergent, or post-treatment-emergent AEs by primary SOC and PT, showing the number (%) of patients (including total patient years in column headers) with at least one AE, will be presented by the internationally agreed SOC order and by decreasing incidence of PTs within each SOC.

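### AESI and selected-AE rates per 100 patient-years count events to last dose + 98 days but divide by exposure that stops at last dose + 14 days

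*SAP*

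**What the plan says.** **The rate.** SAP 2.4.5.1 specifies "The number of events per 100 patient-years (adjusted for the total duration of exposure", for each AESI during the treatment-emergent period. It repeats the rule for AESIs together with the other selected AE groupings: "per 100 patientyears (total number of events adjusted for the total duration of exposure". Protocol 11.4.3.1.2 has the same rule: "Number of treatment-emergent AESIs per 100 patient-years (total number of events adjusted for the total duration of exposure".

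**The event window.** SAP 2.1.4 builds the treatment-emergent period from the treatment epoch, which ends 14 days after the last dose, and the follow-up epoch, which runs from "the date/time of the last dose of IMP + 15 days to the end date of 12-week post-treatment follow-up period". Protocol 11.3.2 puts the end at "up to the last dose of dupilumab plus 2 weeks (corresponding to one dose interval) plus 12 weeks (follow-up period duration", that is, last dose + 98 days.

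**The exposure.** SAP 2.4.3.1 defines duration as the last dose date minus "the first IMP dose date in LTS12551 study + 14 days, regardless of unplanned intermittent discontinuations". The same section adds that "the cumulative duration of treatment exposure, will be provided in patient years by treatment category and overall". Protocol 11.4.1.1 uses the same formula with one dose interval. Neither document defines patient-years that include follow-up. The AE tables are to show total patient-years in their column headers, but the period is not stated.

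**A matched example.** For severe exacerbations, SAP 2.1.3.1 counts onsets up to last dose + 14 days and divides by the last dose date minus "the date of first IMP dose in LTS12551 study + 14 days)/365.25". Events and time end on the same day.

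**The concern.** An event rate needs a numerator and a denominator that cover the same period. Here the 12-week follow-up supplies events and no time, so the rate is too high by an amount that depends on how long the patient was treated. Treatment is 48 or 96 weeks by enrolment date, and the fixed 84 days weigh twice as heavily against 48 weeks as against 96.

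The primary objective is long-term safety, and these are the planned AE event rates that adjust for time. Results for the non-OCS-dependent patients are shown by parent study. Enrolment from DRI12544 was already complete under the amended protocol, so its patients are on the 96-week schedule. Patients from the other parent studies can be on either. Equal true rates could then look different between columns because of the formula alone. Placebo/Dupilumab and Dupilumab/Dupilumab within one parent study should be little affected, since planned duration follows enrolment date.

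**Working it through.** **Inputs.** Treatment of 96 or 48 weeks (Protocol 6.1). EOT visit 2 weeks after the last dose and EOS visit 12 weeks after EOT (Protocol 10.1.1.16, 10.1.1.17, 10.1.2.12, 10.1.2.13). Event window and exposure as set out above.

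**The plan's own durations reproduce.** 96 + 12 = 108 weeks and 48 + 12 = 60 weeks, the maxima in the protocol synopsis (screening excluded). In SAP Table 5, EOT is day 673 and EOS day 757, giving 672 days of exposure and 757 - 673 = 84 days of follow-up.

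**Completers with full follow-up.**

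| Schedule | First to last dose | Exposure (+14) | Event window (+98) | Factor |
|---|---|---|---|---|
| 48-week | 46 × 7 = 322 d | 336 d (0.920 PY) | 420 d (1.150 PY) | 420/336 = 1.25 |
| 96-week | 94 × 7 = 658 d | 672 d (1.840 PY) | 756 d (2.070 PY) | 756/672 = 1.125 |

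**Which reference rate.** Against a rate that divides the same events by the full event window, these factors are exact whenever the events fall. Against a purely on-treatment rate, the factor is 1 + r × 84/exposure, where r is the off-drug rate divided by the on-drug rate. The documents do not give r, so it is an assumption:

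| r | 48-week | 96-week |
|---|---|---|
| 0 | 1.00 | 1.00 |
| 0.5 | 1.125 | 1.063 |
| 1 | 1.25 | 1.125 |
| 2 | 1.50 | 1.25 |

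For that reference, 25% and 12.5% are upper limits for completers only if r is at most 1.

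**Dropout (assumed exponential, proportion d = 10/20/30%, r = 1).** Mean exposure = planned weeks × d / (-ln(1 - d)): 45.6/43.0/40.4 weeks (48-week) and 91.1/86.0/80.7 weeks (96-week).
- All stoppers complete follow-up, 1 + 12/mean: 1.263/1.279/1.297 and 1.132/1.139/1.149.
- Leavers give no follow-up, 1 + (1 - d) × 12/mean: 1.237/1.223/1.208 and 1.119/1.112/1.104.

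Individual early stoppers who complete follow-up have larger factors. For example, 84 days of exposure gives 168/84 = 2.0.

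**Between parent-study columns (completers, equal on-drug rates, all-96-week column as reference).** The documents do not give the 48/96-week split, so it is varied:
- All 48-week, r = 1: 1.25/1.125 = 1.11.
- 80% 48-week, r = 1: mean exposure 0.8 × 48 + 0.2 × 96 = 57.6 weeks; (1 + 12/57.6)/1.125 = 1.208/1.125 = 1.07.
- 50% 48-week, r = 1: mean 72 weeks; (1 + 12/72)/1.125 = 1.167/1.125 = 1.04.
- All 48-week, r = 0.5: 1.125/1.0625 = 1.06.

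**Interim lock (r = 1).** If half the patients have completed follow-up, the rest have none and all have full exposure: 1 + 6/48 = 1.125 and 1 + 6/96 = 1.063. If the half without follow-up has only half the planned exposure: 1 + 6/36 = 1.167 and 1 + 6/72 = 1.083.

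**The case against.** The mismatch and the completer arithmetic are hard to dispute. The case against concerns consequence:

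- **The reading is inferred.** No sentence ties the rate's denominator to SAP 2.4.3.1. True, but that is the only exposure duration defined, and its sum is expressed in patient-years. If another period was meant, the SAP still has to name it.
- **Between-study comparison is not the aim.** SAP version 3 changed the layouts to avoid confounding by between-study variation, and comparisons within a parent study are little affected. That lowers the stakes, but the columns will still stand side by side, and the absolute level and the pooled column are affected too.
- **Some categories are tied to injections.** Injection site reactions and symptomatic overdose with IMP should have few onsets in late follow-up, so r is near 0 and the on-treatment rate is hardly inflated. This stands. It also means that one correction factor cannot be applied across event types afterwards.
- **The 48/96-week mix is undocumented.** This also stands. SAP 1.6 says only that few patients from the later parent studies had data on the discontinued assessments before Amendment 04. The between-column ratios are scenarios.
- **The analysis is descriptive and the error is conservative.** Both are correct. But an overstatement that varies with treatment length and follow-up completeness is not uniformly conservative, and it makes interim and final rates harder to compare.

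**Conclusion.** The concern holds. As written, the rate for AESIs and other selected AE groupings uses an event window up to 84 days longer per patient than its denominator. For completers with full follow-up, the reported rate is 25% (48-week) or 12.5% (96-week) above the matched-window rate. Against an on-treatment rate, the excess reaches those values at r = 1 and falls to zero at r = 0. With the assumed 10–30% dropout and r = 1, the factors run from 1.21 to 1.30 and from 1.10 to 1.15. Apparent ratios between parent-study columns of 1.04 to 1.11 are possible with no true difference, depending on the unknown schedule mix and on r.

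The number and percentage of patients with any TEAE, and the Kaplan-Meier AESI estimates to Week 60, are not affected. Risk is overstated, not hidden. This should be fixed, but it does not threaten the primary result.

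**What to change.** In SAP 2.4.5.1, choose one matched definition and label the tables with it:

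1. **Whole-period rate.** Keep all treatment-emergent events and divide by patient-years from the first LTS12551 dose to the earliest of last dose + 98 days, last contact, death or data cut-off.
2. **On-treatment rate.** Keep exposure as the denominator and count only onsets up to last dose + 14 days, as in SAP 2.1.3.1.

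Option 1 uses all the events, but it dilutes categories that arise only around dosing. With no off-drug events, the completer rate would be 336/420 = 0.80 or 672/756 = 0.89 of the on-treatment rate. Option 2 avoids that but leaves follow-up events out of the rate; they remain in the incidence tables. Either is sound if stated. The SAP should also say that the patient-years in the AE table headers cover the same period.

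The cost is one or two sentences, one derived variable, and an entry in SAP 1.6, because Protocol 11.4.3.1.2 carries the same wording. No new data are needed. Reported rates may be lower than under the present wording.
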